## 3. ANALYSIS SETS AND SUBGROUPS

### 3.1 Analysis sets

The **Enrolled Set (ES)** includes all subjects who have signed the informed consent form.

The **Randomised Set (RS)** includes all subjects randomised at visit VR.

The **Safety Set (SS)** includes all subjects with at least one IMP administration.

The **Full Analysis Set** (FAS) includes all randomised subjects with an evaluable ESS score at the end of at least one treatment period. Evaluability of treatment periods is described in Section 5.6. The efficacy analyses will be conducted on the FAS.

The **Per Protocol** (PP) set includes all subjects in the FAS who have at least one treatment period without a major protocol deviation. Major and minor violations are defined in Sections 5.1.2 and 5.6. The main secondary endpoints (ESS, PVT and cognition) will be analysed with the PP set to demonstrate robustness of the primary analysis.

The **PK analysis set** will include all subjects who have received treatment as per protocol (even if the trial was not completed) and who present no major protocol deviations with an impact on PK.

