### 4.1 General Methodology and Presentation of the Results

The default summary statistics for quantitative (continuous) variables will be

- the number of subjects (n),
- mean,
- standard deviation (SD),
- median,
- first quartile (Q1) and third quartile (Q3)
- minimum (min) and maximum (max)

for subjects with data. Additionally, the geometric mean (GeoMean), geometric standard deviation (GSD), and geometric coefficient of variation (GCV) will be displayed for certain variables. Values of '0' will be removed from the calculation of the geometric mean, GSD, and GCV.

Mean, geometric mean, median, and the quartiles will be presented to one more decimal place than the raw value. The minimum and maximum values will be presented with the same decimal precision as the raw value. SD, GSD, and GCV will be reported to two decimal places greater than the original value.

For qualitative (categorical) variables, the frequency count (n) and percentage (%) of subjects with non-missing data per category will be the default frequency tabulations. Where appropriate and present, the number of missing values will be displayed as "Missing" category.

Percentage values are to be presented to one decimal place, for example, 52.3%.

The denominator used for calculation of the percentages will be specified in a footnote to the tables for clarification.

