## 4.8 Treatment Assignment

In summaries and analyses where data is pooled by treatment, assignment to treatments will be performed as follows:

- Data collected up to and including visit VR (baseline) will be assigned to all treatments.
- Data collected at visits V1A-V1C, V2A-V2C, V3A-V3B, will be assigned to the treatment corresponding to the first, second and third treatment period respectively
- Data collected at the EDV visit will be assigned to treatment periods according to the rules in Section 4.6
- Efficacy analyses will be performed according to treatment **as randomised**. Data will be assigned to treatments based on the combination of planned treatment sequence and treatment period.
- Safety analyses will be performed according to treatment **as treated**. Data will be assigned to treatments based on the treatment actually received during the corresponding treatment period.

Other features of or deviations from the rules of treatment assignment are discussed in the relevant sub-sections of Section 5.

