##### Table 15.1.1.1.S Analysis Sets – Enrolled

##### Table 15.1.1.2.T Analysis Sets – Enrolled

Number and percentage of subjects included into the enrolled, randomised, safety, full analysis, per protocol, and PK analysis sets will be provided. Percentage will be based on the number of subjects in the enrolled set.

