## 5.4 Exposure to IMP and Compliance

### 5.4.1 Exposure to IMP

Exposure data from eCRF includes:

- date of first IMP intake
- date of last IMP intake
- date of IMP dispensed
- number of capsules dispensed (modafinil and flecainide)
- date of IMP returned
- number of capsules returned (modafinil and flecainide)

Exposure data from the subject treatment diaries includes:

- date
- number of capsules taken (modafinil and flecainide)

The **date of first IMP intake** is the intake of the first morning dose as recorded in the eCRF. If the date of first intake as recorded in the eCRF is missing, the first IMP intake recorded in the subjects' diaries will be used.

The **date of last IMP intake** is the date of last IMP intake recorded at trial termination page. If the date of last intake of the last evaluated dose is missing, the last IMP intake recorded in the subject diaries will be used.

The treatment period duration will be calculated in days as follows:

$$\text{treatment period duration (days)} = \text{end-of-treatment visit date} - \text{baseline visit date}$$

For the purposes of treatment period duration calculation, visit VR as well as end-of-washout visits V1C and V2C are considered as baseline visits.

Treatment duration based on IMP exposure data will be calculated for each treatment period as:

$$\text{treatment duration (days)} = \text{last IMP intake date} - \text{first IMP intake date} + 1$$

within the respective treatment period. The overall treatment and treatment period durations will be calculated as the sum of corresponding individual durations.

The following will be provided:

Table 15.1.10.1.1.T Treatment Duration (days) – Safety

Table 15.1.10.1.2.T Treatment Duration (days) – Full Analysis

Table 15.1.10.1.3.T Treatment Duration (days) – Per Protocol

The default summary statistics of treatment period duration and treatment duration will be presented by period and overall.

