- **TEAEs leading to death:** selected as those events where outcome of event is indicated as “fatal”.

The **duration of the AE** will be calculated using the following formula:

$$AE \text{ Duration (days)} = AE \text{ stop date} - AE \text{ start date} + 1$$

If the start or stop dates of the AE are incomplete or AE is still ongoing at the end of the trial, the duration will not be calculated.

The following tables and listings will be provided:

Table 15.2.1.1.1.S Overall Summary of TEAEs – Safety

Table 15.2.1.1.2.T Overall Summary of TEAEs – Safety

An overview of TEAEs:

- TEAE
- Non-Serious TEAE
- Serious TEAE
- Related TEAE
- Related Serious TEAE
- Severe TEAE
- TEAE leading to discontinuation
- Serious TEAE leading to discontinuation
- Related TEAE leading to discontinuation
- TEAE leading to death

will be displayed for the subjects in the safety set.

Table 15.2.1.2.T Incidence of TEAEs – Safety

Table 15.2.1.3.T Incidence of Non-Serious TEAEs – Safety

Table 15.2.1.4.T Incidence of Serious TEAEs – Safety

Table 15.2.1.5.T Incidence of Related TEAEs – Safety

Table 15.2.1.6.T Incidence of Related Serious TEAEs – Safety

Table 15.2.1.7.T Incidence of TEAEs Leading to Discontinuation – Safety

Table 15.2.1.8.T Incidence of TEAEs Leading to Death – Safety

TEAEs will be summarised by displaying the numbers of adverse events, as well as counts and percentages of subjects having experienced adverse events. Percentages will be based on the number of subjects in the safety set. SOC and PTs within each SOC will be ordered by descending overall incidence.

Table 15.2.1.9.T Incidence of TEAEs by Severity – Safety

TEAEs will be summarised similarly as above within each adverse event severity level.

All adverse event data will be listed as follows:

Listing 16.2.6.1 Adverse Events: MedDRA Coding

Listing 16.2.6.2 Adverse Events: General – Enrolled

Listing 16.2.6.3 Serious Adverse Events – Safety

Listing 16.2.6.4 AEs Leading to Discontinuation – Safety

Listing 16.2.6.5 AEs Leading to Death – Safety

All AEs will be displayed by subject including the PT of an AE, start and stop dates, duration and other characteristics of AEs.

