## 5.5.2 Clinical Laboratory Evaluation

Clinical laboratory values (haematology, biochemistry, and urinalysis) are collected at visit VS1, VR, V1B, V2B, and V3B/EDV for each laboratory parameter.

The following parameters are collected:

**Haematology:** Leukocytes, erythrocytes, haemoglobin, haematocrit, MCV, MCH, platelets, neutrophils, lymphocytes, monocytes, eosinophils, basophils, neutrophils (%), lymphocytes (%), monocytes (%), eosinophils (%), basophils (%).

**Biochemistry:** sodium, potassium, urea, creatinine, total protein, albumin, total bilirubin, direct bilirubin, AST (GOT), ALT (GPT), alkaline phosphatase, uric acid, glucose (fasting and non-fasting), cholesterol, triglycerides.

**Urinalysis:** Leukocytes, nitrites, pH, protein, glucose, ketones, urobilinogen, bilirubin, blood, haemoglobin.

Haematology and biochemistry test results are assigned an LNH classification according to whether the value is lower than (L), within (N) or higher than (H) the reference range for that parameter as provided by the corresponding laboratory.

Clinical significance of laboratory values is evaluated by the investigator.

Range values of laboratory results will be set to ½ of the specified threshold for analysis (e.g. a result of “<0.03” will be considered as 0.015 in summaries).

The following tables and listings will be provided:

Table 15.2.4.1.1.T Summary of Clinical Laboratory Tests: Haematology – Safety

Table 15.2.4.1.2.T Summary of Clinical Laboratory Tests: Biochemistry – Safety

Table 15.2.4.1.3.T Summary of Clinical Laboratory Tests: Urinalysis – Safety

The default summary statistics of clinical laboratory test results will be presented at each visit. The absolute change from baseline will be presented for haematology and biochemistry findings.

Table 15.2.4.2.1.T Clinical Laboratory Tests: Incidence of Haematology Abnormalities – Safety

Table 15.2.4.2.2.T Clinical Laboratory Tests: Incidence of Biochemistry Abnormalities – Safety

Number and percentage of subjects for each laboratory parameter will be displayed in CS Low, Low, Normal, High, and CS High categories. Percentage will be based on the number of subjects at specified visit.

Table 15.2.4.2.3.T Clinical Laboratory Tests: Incidence of Urinalysis Abnormalities – Safety

Number and percentage of subjects with abnormal values of urinalysis parameters will be displayed in normal/abnormal/CS abnormal categories. Percentage will be based on the number of subjects at specified visit.

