## 9. APPENDICES

The following documents are attached as appendices to the SAP:

1. THN102\_202\_AX3\_Analysis\_Plan\_Draft\_1.3\_20200115
2. THN102-202\_Table\_Shells\_Final1.0\_2020\_02\_21.docx
3. THN102-202\_Listing\_Shells\_Final1.0\_2020\_02\_21.docx
4. THN102-202\_Figure\_Shells\_Final1.0\_2020\_02\_21.docx

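### SAP 5.5.1 defines discontinuation TEAEs partly by a code absent from its own field list; the percentage base of the by-treatment TEAE tables also needs rewording

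*SAP*

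**What the plan says.** **Discontinuation.** SAP 5.5.1 lists the values collected for each AE. Action taken with IMP has four: no action, interrupted, withdrawn, unknown. Other actions has five: none, medication, tests, hospitalisation (required or prolonged), and other. The section then defines TEAEs leading to discontinuation as those with IMP action *drug withdrawn* or other action *withdrawal from trial*. The definition feeds three rows of the TEAE overview (all, serious and related TEAEs leading to discontinuation) and Table 15.2.1.7.T. No other definition is given for Listing 16.2.6.4. Separately, SAP 5.1.1 collects a reason for premature termination, with adverse event as one option, and shows it in the disposition tables and in Listings 16.2.1.2 and 16.2.1.3.

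**Percentage base.** For Tables 15.2.1.2.T to 15.2.1.8.T, SAP 5.5.1 says: "Percentages will be based on the number of subjects in the safety set". Table 15.2.1.9.T follows the same method. The .T suffix marks tables shown by treatment (SAP 4.3). Under SAP 3.1 the Safety Set "includes all subjects with at least one IMP administration", and no per-treatment version is defined. Under SAP 4.8, safety data go to the treatment received: "Data will be assigned to treatments based on the treatment actually received during the corresponding treatment period". SAP 5.5.1 places a TEAE in the treatment period containing its onset, and a washout onset in the preceding period.

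**The concern.** Safety versus placebo is the primary objective, and AEs that end participation are among the outputs a reader consults first. If one of the two routes into that category depends on a code that cannot be entered, the category is narrower than the definition intends. The exposed cases are subjects who leave because of an AE while the action with IMP is recorded as something other than withdrawn. Washout is the clearest setting: no IMP is being taken, so the investigator may not record it as withdrawn, yet the event is treatment-emergent and belongs to the preceding treatment. The AE tables could then report fewer discontinuations than the disposition tables, with no rule in the SAP for reconciling them.

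The percentage base raises a smaller question. The numerator is specific to a treatment, while the stated denominator, taken at its word, is the same trial-wide set in every column. In a three-period crossover without replacement of drop-outs (Protocol 4.1), the two differ as soon as someone leaves before reaching a treatment.

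**Working it through.** The plan gives no figure for either matter, so there is none to reproduce.

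**Discontinuation: the definition against the field lists (all SAP 5.5.1)**

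- Route 1, IMP action *drug withdrawn*: one of the four listed values, so it can be met.
- Route 2, other action *withdrawal from trial*: matches 0 of the five listed values.
- Mapping from *other*: none stated. The neighbouring definitions do carry such rules: missing relationship counts as related and missing severity as severe.
- Result on the listed codes: only route 1 selects anything. An AE that ends participation with IMP action recorded as no action, interrupted or unknown is not selected. The documents give no rate for such cases, so no size can be computed.

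**Percentage base: literal reading**

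Inputs: 60 planned for safety and 54 evaluable for efficacy (Protocol synopsis); 54 as the target for completion per protocol, without replacement (Protocol 4.1).

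Assumption: k, the number of safety-set subjects who never took a given treatment, lies between 0 and 60 − 54 = 6. The documents give neither the timing of drop-out nor its distribution over treatments.

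Formulas: exposed N = 60 − k; shown rate = true rate × (60 − k)/60; relative understatement = 1 − (60 − k)/60 = k/60, which is 1/60 = 1.7% per subject.

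Treatments missed per drop-out: 2 if leaving in period I or washout I, 1 if in period II or washout II, 0 if in period III.

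| Assumed pattern | k per treatment | Exposed N | Understatement | True 30% shows as | True 10% shows as |
|---|---|---|---|---|---|
| No subject misses the treatment | 0 | 60 | 0% | 30.0% | 10.0% |
| Six drop-outs, two per period, even over treatments | (2×2 + 2×1 + 2×0)/3 = 2 | 58 | 2/60 = 3.3% | 29.0% | 9.7% |
| All six gone before period II, even over treatments | (6×2)/3 = 4 | 56 | 4/60 = 6.7% | 28.0% | 9.3% |
| All six miss the same treatment | 6 | 54 | 6/60 = 10% | 27.0% | 9.0% |

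Equal k shrinks all columns by the same factor. Unequal k distorts the comparison. If all six left after taking Dose C in period I, exposed N would be 54, 54 and 60 for A, B and C, and a true 20% everywhere would show as 18.0%, 18.0% and 20.0%. If three left after B and three after C in period I, N would be 54, 57 and 57, and 20% would show as 18.0%, 19.0% and 19.0%.

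**The case against.** **On the percentage base**, the other side is strong.

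- The sentence looks like standard text naming an analysis set. SAP 5.1.1 attaches the same base to the Enrolled site table, where it cannot be literal (72/60 = 120% at planned numbers), and to the Randomised disposition table.
- By-sequence tables elsewhere use a similar phrase about the respective set, and the natural reading is the set's members in that column. Read the same way, the TEAE tables contain no error.
- SAP 5.1.1 plans Table 15.1.1.2.T by treatment: "Number and percentage of subjects included into the enrolled, randomised, safety, full analysis, per protocol, and PK analysis sets will be provided". SAP 5.4.1 also plans by-treatment exposure: "The default summary statistics of treatment period duration and treatment duration will be presented by period and overall".
- SAP 4.1 promises that "The denominator used for calculation of the percentages will be specified in a footnote to the tables for clarification". The table shells are among the documents introduced in SAP section 9 by "The following documents are attached as appendices to the SAP", but they are not shown.
- Laboratory abnormalities use a different base, "Percentage will be based on the number of subjects at specified visit", but those are visit-level tables. A visit count would not suit AE tables that accumulate over a period.

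Most of this stands. A per-column N is plausible and may already be programmed. What remains is that no section states it: the planned counts give no membership rule or AE percentage base, and a promised footnote says where the base will appear, not what it is.

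**On discontinuation**, *drug withdrawn* should capture most AEs that stop IMP during a treatment period, and *other* may carry free text on an eCRF page that is not shown. Termination reasons are tabulated and listed, Protocol 4.4.2 requires follow-up to establish whether an AE was the reason, and all AEs are listed. These limit the consequence. They do not supply the missing mapping.

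**Conclusion.** The discontinuation definition does not match the values that the same section says are collected. As written, its second branch selects nothing from the listed codes. This is a minor internal inconsistency whose size the documents do not allow one to compute. A reader might infer that discontinuations due to AEs would vanish from the report. The documents do not support that, because disposition and the full AE listings would still show them. The exposure is an undercount in the named AE outputs and a possible disagreement with disposition.

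The percentage base is a wording correction. At the planned 60, with six drop-outs assumed, the literal reading understates a treatment's rate by 3.3% in relative terms under even spread and by 10% only in the extreme case. The effect is zero if the shells use a per-column N. Two stronger readings should be resisted:

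- That the reported percentages are wrong. The shells and footnotes are not shown, so the documents do not establish what was programmed.
- That 10% is the expected size, or that the error favours THN102. The figure of 54 is a target for completing per protocol, not an exposure count: a subject can miss it after taking all three treatments. The direction depends on who leaves and when. In both unequal patterns above, the placebo column shrinks at least as much as either active column.

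The denominator wording leaves event and subject counts unaffected. Safety is descriptive, and no test or decision rule depends on either point.

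**What to change.** 1. In SAP 5.5.1, align the discontinuation definition with the collected values: *drug withdrawn*, or *other* where recorded text, if collected, indicates withdrawal from the trial. Before unblinding, compare the selected subjects with those whose termination reason is adverse event (Listings 16.2.1.2 and 16.2.1.3), and resolve and document mismatches.
2. Reword the percentage sentence so that, in the .T AE tables, N and the base are the safety-set subjects with at least one intake of that treatment, as treated, with N in the column header. Confirm that the shells match; if they already do, only the sentence changes.

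Cost: two SAP sentences, a column N if not already programmed, and no new data collection. The blind data review meeting was held on 10-FEB-2020, before the SAP was finalised, so the reconciliation needs a short separate blinded check documented by addendum. Counts could change only in the discontinuation outputs, if the check finds omitted cases.

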## 5.5.2 Clinical Laboratory Evaluation

Clinical laboratory values (haematology, biochemistry, and urinalysis) are collected at visit VS1, VR, V1B, V2B, and V3B/EDV for each laboratory parameter.

The following parameters are collected:

**Haematology:** Leukocytes, erythrocytes, haemoglobin, haematocrit, MCV, MCH, platelets, neutrophils, lymphocytes, monocytes, eosinophils, basophils, neutrophils (%), lymphocytes (%), monocytes (%), eosinophils (%), basophils (%).

**Biochemistry:** sodium, potassium, urea, creatinine, total protein, albumin, total bilirubin, direct bilirubin, AST (GOT), ALT (GPT), alkaline phosphatase, uric acid, glucose (fasting and non-fasting), cholesterol, triglycerides.

**Urinalysis:** Leukocytes, nitrites, pH, protein, glucose, ketones, urobilinogen, bilirubin, blood, haemoglobin.

Haematology and biochemistry test results are assigned an LNH classification according to whether the value is lower than (L), within (N) or higher than (H) the reference range for that parameter as provided by the corresponding laboratory.

Clinical significance of laboratory values is evaluated by the investigator.

Range values of laboratory results will be set to ½ of the specified threshold for analysis (e.g. a result of “<0.03” will be considered as 0.015 in summaries).

The following tables and listings will be provided:

Table 15.2.4.1.1.T Summary of Clinical Laboratory Tests: Haematology – Safety

Table 15.2.4.1.2.T Summary of Clinical Laboratory Tests: Biochemistry – Safety

Table 15.2.4.1.3.T Summary of Clinical Laboratory Tests: Urinalysis – Safety

The default summary statistics of clinical laboratory test results will be presented at each visit. The absolute change from baseline will be presented for haematology and biochemistry findings.

Table 15.2.4.2.1.T Clinical Laboratory Tests: Incidence of Haematology Abnormalities – Safety

Table 15.2.4.2.2.T Clinical Laboratory Tests: Incidence of Biochemistry Abnormalities – Safety

Number and percentage of subjects for each laboratory parameter will be displayed in CS Low, Low, Normal, High, and CS High categories. Percentage will be based on the number of subjects at specified visit.

Table 15.2.4.2.3.T Clinical Laboratory Tests: Incidence of Urinalysis Abnormalities – Safety

Number and percentage of subjects with abnormal values of urinalysis parameters will be displayed in normal/abnormal/CS abnormal categories. Percentage will be based on the number of subjects at specified visit.

Table 15.2.4.3.1.T Clinical Laboratory Tests: Shift Table of Haematology Results – Safety

Table 15.2.4.3.2.T Clinical Laboratory Tests: Shift Table of Biochemistry Results – Safety

Table 15.2.4.3.3.T Clinical Laboratory Tests: Shift Table of Urinalysis Results – Safety

Shift tables showing changes in the number and frequency of subjects with respect to the normal range between baseline and endpoint will be provided. Subjects with missing data will be presented as part of a “missing” category.

Listing 16.2.7.1 Laboratory Data – Haematology – Enrolled

Listing 16.2.7.2 Laboratory Data – Biochemistry – Enrolled

Values of laboratory tests will be listed.

Listing 16.2.7.3 Laboratory Data – Urinalysis – Enrolled

All urinalysis data will be listed.

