## 5.1.2 Protocol Deviations

All analysis sets are defined in Section **Error! Reference source not found.**. The per protocol (PP) set is defined as all subjects who have completed the trial without major protocol deviation.

During the Blind Data Review (BDR) the eligibility of subjects for the PP set will be assessed. The BDR will be performed after data entry, prior to locking the database. All decisions made during the BDR will be documented in the BDR report before the closure of the database.

Protocol deviations are deviations from the procedures outlined in the clinical trial protocol or from subsequent protocol-related instructions like missed evaluations, incorrect timing of evaluations, non-compliance with the IMP, intake of prohibited medications or any non-adherence to the clinical trial protocol that impacts subject's rights, safety or welfare. Protocol deviations that may affect the efficacy or PK outcome will be discussed during the BDR.

An appropriate clinical trial team, including a physician, will review potential protocol deviations and relevant information regarding those deviations to determine a possible impact on safety or efficacy endpoints. A decision will be made as to the effect of the possible deviations to determine if it is considered major or minor. The status, major or minor, of each protocol deviation will be documented in the BDR report. A subject may have one or more major protocol deviations resulting in the exclusion of that subject from the per protocol analysis set.

Reference listings will also be made available to help with the review of the protocol deviations.

Note: Protocol deviations will, if possible, be validated against data recorded in the eCRF. Note where an answer for an inclusion/exclusion tick box differs from the algorithmic check of the criteria, the algorithmic check will overrule the tick box.

Protocol deviations of the following categories and respective data listings will be reviewed during the BDR.

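### The SAP's halving rule for laboratory range values is not limited to '<x' results; read literally, it analyses a '>x' result as x/2, below its known lower bound (minor)

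*SAP*

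**What the plan says.** SAP 5.5.2 (Clinical Laboratory Evaluation) has one substitution rule for laboratory results that are reported as a bound instead of a number: "Range values of laboratory results will be set to ½ of the specified threshold for analysis". Its one illustration is a below-limit result of <0.03, which "will be considered as 0.015 in summaries".

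The same section says where the numbers go: "The default summary statistics of clinical laboratory test results will be presented at each visit", and "The absolute change from baseline will be presented for haematology and biochemistry findings". These are Tables 15.2.4.1.1.T to 15.2.4.1.3.T. Under SAP 4.1 the default statistics include the mean, median, quartiles, minimum and maximum.

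Three other statements in SAP 5.5.2 bear on how far the rule reaches:

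- "Haematology and biochemistry test results are assigned an LNH classification" against the laboratory's reference range. The section does not say whether this happens before or after substitution.
- "Clinical significance of laboratory values is evaluated by the investigator".
- "Values of laboratory tests will be listed". Nothing is said about halving in the listings.

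No other passage fills the gap. SAP 7 (changes from the protocol) records only the new Per Protocol definition. Protocol 8.3.3 has a separate rule for concentrations above the upper limit of quantification, but it covers pharmacokinetic data only.

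**The concern.** Half the threshold is a conventional stand-in for '<x', because x/2 lies inside the range where the true value can be. For '>x' the same number lies outside that range: the assay has already shown that the value is above x. A programmer who follows the sentence literally puts an impossible value into the summaries. One who does not follow it has to invent a rule that the signed-off plan does not contain.

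The trial's primary objective is the safety profile, and the safety laboratory is a listed safety endpoint (SAP 2.1.1 and 2.2.1). A reader of the laboratory tables will look at the maximum and the change from baseline, and those are the statistics that one mis-set high value distorts most.

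**Working it through.** **1. The plan's own figure.** Substituted value = threshold/2. For <0.03: 0.03/2 = 0.015, which matches the SAP.

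**2. The same rule applied to '>x'.** Let T be the true value, so T > x. The analysed value is x/2 and the shortfall is T − x/2. Since x/2 < T/2, the shortfall is more than T/2, that is, more than 50% of the true value. In absolute terms it exceeds x/2.

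**3. Change from baseline.** This depends on which visit has the '>x' result.

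- Post-baseline '>x', baseline b: the true change is above x − b and the analysed change is x/2 − b, so it is too low by more than x/2. If b lies between x/2 and x, a rise is shown as a fall. With an assumed threshold of 200 and b = 120, the true change exceeds 200 − 120 = +80, while the analysed change is 100 − 120 = −20.
- Baseline '>x', later value p: the true change is below p − x and the analysed change is p − x/2, so it is too high by more than x/2. If p lies between x/2 and x, a fall is shown as a rise. Because SAP 4.8 assigns baseline data to all treatments, this error enters every treatment that the subject receives.

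**4. Size in the tables.** The documents give no upper reporting limits, so x is assumed here as a multiple of the upper limit of normal (ULN). One '>x' result among n values lowers the mean by (x/2)/n compared with using x. With n = 60 (all randomised subjects) this is x/120. If each visit is shown separately within treatment, balanced allocation gives 60/3 = 20 subjects per cell, and the effect is x/40.

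| Assumed x (ULN) | Analysed as x/2 (ULN) | Mean lowered, n = 60 (ULN) | Mean lowered, n = 20 (ULN) |
|---|---|---|---|
| 1.5 | 0.75 | 0.0125 | 0.0375 |
| 2 | 1.0 | 0.0167 | 0.05 |
| 3 | 1.5 | 0.0250 | 0.075 |
| 5 | 2.5 | 0.0417 | 0.125 |
| 10 | 5.0 | 0.0833 | 0.25 |

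The true maximum is above x, but the table would show the larger of x/2 and the highest other value.

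**5. Classification tables.** The incidence tables (15.2.4.2.x) and shift tables (15.2.4.3.x) use categories, not means. They change only if low/normal/high is derived from the substituted number. In that case a '>x' result with x at or below 2 ULN would fall to the ULN or lower. Above 2 ULN it would still count as high.

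**The case against.** The best defence is that the sentence should be read with its example. Read that way it is an ordinary half-limit rule for below-limit results, which merely leaves '>x' unmentioned. The authors may well have meant this. But an example illustrates a rule without limiting it, and on the narrower reading the plan has no rule at all for '>x' safety results. The sentence needs a direction on either reading.

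The defence is also right that the outputs most used to detect a safety signal are largely protected. Investigators judge clinical significance themselves. Under Protocol 6.3.2 a change to a clinically significant abnormal value is recorded as an adverse event, unless it is a laboratory error or the underlying disease is already documented. Values are listed by subject, and no hypothesis test uses these data. This limits the consequence but does not make x/2 a valid value.

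A reader might infer that the error always flatters the drug. It does not. A '>x' result at baseline inflates the later change, and for parameters where a low value is the worry, such as albumin or platelets, halving would look alarming.

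**Conclusion.** Wrong as written, and minor. Taken literally, SAP 5.5.2 replaces a '>x' laboratory result with a value that the result itself excludes. The error is more than 50% of that value. It is more than x/2 in that subject's change from baseline, in either direction, when one of the two results is a '>x' result. The certain effect is limited to Tables 15.2.4.1.x. Any effect on the incidence and shift tables depends on an order of derivation that the SAP leaves open.

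The effect on means rests on assumed thresholds. The documents do not show whether any '>x' result occurs, and such results are probably few.

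A reader might also infer that halving could create false eligibility deviations, for example by turning a glomerular filtration rate reported as above 90 into 45, below the limit of 60 in exclusion criterion 9. The documents do not support this:

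- Protocol 6.2.5 calculates the rate from creatinine by equation, which yields a number.
- SAP 5.5.9.2 treats it as a screening item that is only listed.
- SAP 5.1.2 checks deviations against recorded eCRF data and marks this criterion for case-by-case review.
- Nothing sends substituted summary values into eligibility checks.

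**What to change.** Replace the sentence in SAP 5.5.2 with:

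> Results reported as <x are set to x/2; results reported as >x are set to x, for numeric summaries only; L/N/H and clinical-significance classes use the reported result.

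Setting '>x' to x still understates the true value by an unknown amount, but x is the known lower bound and is never on the wrong side of it. The SAP's own example stays at 0.015.

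The cost is one SAP sentence. It should be settled before unblinding, so that the handling of such results is not chosen with the treatment codes known.
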